Beyond non-contact thermographic screening, deeper concerns for public health have arisen with a related non-contact technology. Specifically, the concern is with an existing FDA-approved class of non-contact single pixel (single pixel meaning non-thermographic, or non-image-based) infrared (IR) scanning systems configured to perform IR temperature measurements of the forehead and report an extrapolated core body temperature. FDA-approved devices within this class have been observed to report healthy body temperatures in conditions that should preclude an accurate measurement (e.g. being operated outdoors in inclement conditions), which has led to many clinicians being wary of trusting these devices. Furthermore these devices have also been observed to report temperatures all within a

normal range between 97 and 99F when operated on an IR calibration source having simulated body temperatures covering the range from 95F to 103F, which is a clear cause for concern. This specific observation has led to published reports documenting the use of “bias-to-normal” algorithms that take a range of input temperature measurements and output a smaller range of temperatures closer to the normal body temperature. This is difficult to detect due to the limited spread in normal core body temperatures in the healthy population, and in fact, by generating a made-up temperature from 98.6 plus or minus a small random fraction less than 1, one can produce an apparently-functional body temperature measurement system that is difficult to distinguish from the oral temperature measurement. Due to the presence of documented bias-to-normal algorithms, it is clear that improvements in test methods are desperately needed. Until such time, any evaluation must include a range of actual core body temperatures extending into diagnostically-relevant high temperatures (individuals having real fevers) or it will be difficult to detect a bias-to-normal algorithm.

[figure not shown]

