In a second analysis, the equilibration time constants will be evaluated for possible linear correlations with the demographic data, although it is possible the small sample size and variability will preclude the detection of any significant correlations. In case there are nonlinear relations, scatter plots will be examined to determine if a low-order polynomial or other reasonable fit could explain a relation, while keeping in mind the fact each additional test is a multiple comparison, thus increasing the required p-value multiplicatively. Scatter-plots, trends and r-values will be reported, and this data may be collated with future collections of independent datasets.

The controlled face temperature data will be analyzed for sensitivity and specificity of each non-contact system used, first in a blinded analysis and then in an open-label analysis. First, the blinded face temperature data will be used to assign each recorded datapoint into normal, mild and moderate and severe fever groups, corresponding to below 38C (100.4F), 38-39C (100.4-102.2F), 39-40C (102.2-104F) and above 40C (104F). Note, the heated rooms' air temperatures were selected to produce simulated core temperatures that straddle the mild and moderate thresholds (hence, a well-performing system should place 50% of the measurements above the threshold and 50% below while a system relying on a bias-to-normal method might place only 10% above the selected threshold), therefore the severe fevers group

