should likewise have few subjects placed within it. The sensitivity and specificity for assessing each of a mild and a moderate fever temperature will be assessed in a straightforward manner by revealing the labels and determining the fractions of correctly- and incorrectly-labelled datasets. These labels are generated by first matching the NFC UUID associated with an *nfc-temperature-scan* to the previous closest in time *nfc-room-scan* of this same NFC UUID and taking that room's air temperature difference to the temperature scanner's air temperature and converting to simulated core body temperature. Next, this now open-label data will be used to determine the mean and standard deviation across the core temperature scans of each of these four groups. The standard deviation of oral temperatures below the 38C threshold will be used to determine the false positive rate, using an assumed normal distribution or a low-dimensional parametric fit to the actual oral distribution. A parametric fit to the distribution above 38C will be used to determine the sensitivity and specificity for mild, moderate and severe fever thresholds, corresponding to 38-39C, 39-40C and 40C and above, respectively, using the sum of the area under the curve above the appropriate threshold. The linear correlation between oral and imaging temperatures in the below-threshold range will be tested for significance. A subset of the data consisting of equal parts of over-threshold (fevers, by oral temperatures) and under-threshold participants will be tested for significance, and this significance level compared with that of the whole set.

In a second analysis, the controlled face temperature data will be analyzed for effect of confounds with the primary non-contact thermographic system. In this case, the physiologic correction parameters obtained from each individual will be examined for linear correlates or nonlinear relationships with the demographic data. As with the equilibration data, scatter-plots, trends and r-values will be reported, and this data may be collated with future collections of independent datasets.

Quality control and data management

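### The parametric false positive rate in Section D is taken from oral temperatures, so as written it is not specific to any non-contact system

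*Combined protocol and SAP*

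**What the plan says.** Section D states that the controlled face temperature data "will be analyzed for sensitivity and specificity of each non-contact system used". Two routes follow.

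- **Label-based step.** Room labels are revealed, and sensitivity and specificity come from "determining the fractions of correctly- and incorrectly-labelled datasets". This uses each system's own readings.
- **Open-label parametric step.** The plan first takes the "mean and standard deviation across the core temperature scans of each of these four groups". The next sentence reads: "The standard deviation of oral temperatures below the 38C threshold will be used to determine the false positive rate", using either a normal distribution or a low-dimensional fit to the oral distribution actually observed.

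The threshold is fixed at 38C (100.4F) for all systems. Under Oral Thermometry in Section B, an oral reading follows each set of non-contact measurements, so the systems used on a visit share the same oral reading.

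**The concern.** A system's false positive rate is the probability that its own reading exceeds the threshold when the true, or labelled, temperature is below it. It depends on the device's bias and spread. The quoted sentence builds the rate from the spread of the reference thermometer and a fixed threshold. Neither changes when one device is swapped for another.

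Followed as written, the step gives one number that would be read as a property of every system tested. A system that reads too high, and so flags many afebrile people, would get the same low rate as an accurate one. The study is meant to help identify devices that operate improperly, so this error matters for a figure that may be published for each system.

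**Working it through.** The plan states no numerical false positive rate, so there is no figure to reproduce. The check applies the sentence as written and then applies the same formula to device readings.

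**Inputs**
- Threshold T = 100.4F (Section D).
- Oral mean 97.9F to 98.6F and SD about 1F, also given as 0.6C = 1.08F (Section A, Introduction).
- Primary-system SD 1.11F (Section B, Population Size). This is the total spread of past readings, including core variability, obtained under less controlled conditions.
- Device bias: not in the documents. Values of 0, +0.5F and +0.9F are assumed.

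**Formula.** Rate = 1 - Φ((T - mean)/SD).

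**Step 1: as the plan is written (oral mean and SD)**

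| Oral mean | SD | z | Rate |
|---|---|---|---|
| 97.9F | 1F | 2.50 | 0.6% |
| 98.6F | 1F | 1.80 | 3.6% |
| 97.9F | 1.08F | 2.31 | 1.0% |
| 98.6F | 1.08F | 1.67 | 4.8% |

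The plan uses only oral values below 38C, which truncates the distribution. For a true mean of 98.6F and SD 1F, the truncated mean and SD are 98.52F and 0.92F, and the refitted tail is 2.0%. For a mean of 97.9F they are 97.88F and 0.978F, and the tail is 0.5%. In every row the device is absent, so the result holds for all systems alike.

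**Step 2: the same formula on a device's own readings (SD 1.11F)**

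| True mean | Bias | z | Rate |
|---|---|---|---|
| 98.6F | 0 | 1.62 | 5.2% |
| 98.6F | +0.5F | 1.17 | 12.1% |
| 98.6F | +0.9F | 0.81 | 20.9% |
| 97.9F | 0 | 2.25 | 1.2% |
| 97.9F | +0.5F | 1.80 | 3.6% |
| 97.9F | +0.9F | 1.44 | 7.5% |

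**Comparison.** At a true mean of 98.6F the plan's step returns 3.6% (oral SD 1F) for all three devices, whose own rates are 5.2%, 12.1% and 20.9%. For the unbiased device the gap is modest. For the over-reading device it is large: 20.9% against 3.6%.

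**The case against.** **The aim is already met by the label-based step.** That step is device-specific and comes first. This stands, and it limits the point to one later sentence. A reader might infer that Section D yields no valid specificity for any system. The documents do not support that: the label-based fractions, and the check that a good system puts about half of the heated-room readings above threshold against perhaps 10% for a biased one, do not use the oral SD.

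**The sentence may mean something else.** The scan mean and SD in the sentence before it might be intended as inputs, or oral might mean a device's oral-equivalent output. The text makes no such link, it speaks of the actual oral distribution, and shortly afterwards it contrasts oral with imaging temperatures. If a device mean were paired with the oral SD, the device's own spread would still be ignored. Rates could differ slightly between systems if oral data were restricted to visits with a valid scan on each system. The plan describes no such step, and the rate would still not measure the device.

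**The size can be overstated.** A reader might infer that the parametric and label-based rates differ several-fold even for an unbiased system because oral data replace device data. That does not follow. Take labels of 98.6F + 0.236 × (room air - 68F), room air varying uniformly by 1.0F to 1.8F around the setpoint, and device SD 1.11F. Room A scans alone give about 5.4% to 5.7%. The rate over all label-negative scans rises to about 18% to 19% only because roughly half of Room B visits carry labels just under the threshold (42% to 46% positive). The design intends this, since the heated rooms are meant to "straddle the mild and moderate thresholds". Most of that gap is case mix.

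**Bias toward normal.** A reader might also infer that a corrected rate would expose the device imagined in the Introduction, which works "by generating a made-up temperature from 98.6 plus or minus a small random fraction less than 1". It would not. Such readings never reach 100.4F, so that device's correct false positive rate is 0%. Its failure shows in sensitivity and in the 50% versus 10% check.

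**Conclusion.** The point holds for the parametric step of Section D only. On the natural reading, the false positive rate there describes the reference thermometer, is common to all systems scanned on the same visits, and cannot stand as 1 - specificity of a system. That conclusion needs no numerical assumption.

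The size is illustrative. The rate would be about 0.6% to 3.6% for any device (oral SD 1F), against about 5% for an unbiased device and about 21% for one over-reading by 0.9F, both at a true mean of 98.6F. These figures assume normality, a device SD of 1.11F borrowed from less controlled past data, and biases that the documents do not give. The practical harm is false reassurance about an over-reading system. The label-based results are sound on this point and should stay as they are.

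**What to change.** Reword the sentence in Section D. For each system, fit that system's own readings among all scans labelled below the threshold, including label-negative visits to the heated rooms, and take the false positive rate from that fit.

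Alternatively, delete the parametric false positive rate and rely on the label-based specificity already planned.

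Either change costs one or two sentences in Section D. No new data, visits or participants are needed, because the scans and room labels are already collected.

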Research Protocol

Title: Investigation of the effect of environmental temperatures on non-contact thermal imaging for core body temperature measurement

Principal Investigator: [name]

Co-Investigators: [name] PhD, [name] PhD, [name]

A. Introduction

The purpose of this study is to examine the effect of the local environment and the physiology of the human body on the relationship between core body temperature and inner canthus (region near tear duct) skin temperature measured using non-contact thermal imaging. The overall goal of this research study is to validate and improve the science of non-contact core body temperature measurement. The present inquiry is of minimal or no risk, is not focused on a vulnerable population, will include study participants who are not current members of the St. Olaf community and findings will be shared outside St. Olaf, thus this is a Type 2 project.

Core body temperature is one of the vital signs, being used to diagnose conditions associated with abnormally high or low temperatures. Normal body temperature can vary with gender, recent activity, food and fluid consumption, mental and physical stress, time of day, and, in women, the stage of the menstrual cycle¹. Clinical studies of oral temperatures acquired using thermometers having a measurement accuracy of 0.1C (0.18F) in healthy adult humans have found a distribution with a standard deviation of approximately 1F (0.6C) and averages ranging from 97.9F to 98.6F². Oral thermometry is sensitive to probe placement, recent speaking or mouth-breathing, recent fluid or food consumption and even air temperature. In-ear thermometry is an oft-used alternative but is affected by ear geometry and debris, often requiring re-measurement attempts. These thermometry methods can be inconvenient in some clinical practices due to the time required, and thus, non-contact or other surface-based thermometry methods are desired.

The use of non-contact core temperature screening has become widespread in society due to the COVID-19 pandemic. Past clinical trials have demonstrated the sensitivity and accuracy of thermographic (image-based) non-contact body temperature measurement. A comprehensive

¹ Normal physiologic variability in core temperature is well established, with the time-of-day and menstrual cycle generally accepted as contributing the largest sources of variability, each ranging from 0.3 to 1F in magnitude.

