Given the difficulty of obtaining sufficient febrile participants for assessing these systems, it would be ideal if there were a way of objectively manipulating face temperatures, however until now simple methods such as heated water bottles have had accuracy of at best 5 degrees C, which is too poor for the assessment of these systems in the way they are intended to be used. As a consequence, regulatory agencies and users have not had a way to assess these systems. Based on recent findings, it is possible that nearly all or even all body temperature measurement systems used to-date have relied on bias-to-normal methods due to major confounds. If there were a source of faces with varying temperatures corresponding to mild, moderate and severe fevers as well as healthy temperatures, it would become possible to detect biasing methods. A new method, used in this study, allows the objective manipulation of face temperatures with sufficient accuracy for assessing real-world sensitivity and specificity.

Furthermore, this method requires no special equipment beyond a clinical oral thermometer and control over air temperatures in closed spaces (rooms, large tents having sufficient dimensions for multiple persons to stand, or other controllable spaces, hereafter “rooms”) to within 1C and allows the control of simulated body temperatures with 0.25C accuracy.

The image on the left shows a thermographic core body measurement system that incorporates dual IR calibration sources in the imaging field of view. The image on the right shows general positioning and usage for different height individuals. Once a face is detected within the field of view, the camera collects thermal images which have been corrected for luminance artifact and linearized to the IR calibration sources, and typically reports a core temperature estimate within a second, reporting the result on the display.

The images above show a typical thermal face image as captured by the system, with the results of an automatic thermal face detection system overlain on the subject's face. Below the subject's face and to the sides are the two IR reference targets. It is important to point out that thermal light does not penetrate clothing or common objects such as glass and plastic that is

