Participants will be recruited from the population of summer students, faculty and staff at St Olaf college and responders to the St Olaf-affiliated email list during the summer of 2021. The research study will be advertised in three ways: 1) via selected campus email lists created for summer research students, students working on campus over summer and international students living on campus or nearby over summer, 2) via faculty and staff email lists, the St Olaf-affiliated list stolaf-extra and the Psychology 125 Moodle site and 3) via posted advertisements in up to two areas allowing physical postings each in Buntrock Commons, the Athletic Center, the Science Center and residence halls, e.g. outside the Caf in Buntrock Commons, near the main entry to the Athletic Center. The exact advertisements are included as supplementary materials to the protocol along with an advertisement protocol denoting the timing and duration of each advertisement.

Participants responding to the advertisement will be briefly interviewed to determine their potential status regarding the inclusion and exclusion criteria and timing available for the study completion. Participants will be in common areas, in sufficiently close proximity to each other (respecting COVID-19 social distancing) to enable conversation and potentially revealing information to each other, which the study personnel will have little to no control over. The participants will be made aware of this possibility and told to refrain from disclosing personal

information in the consent document. Participants will be informed of the requirement to wear masks at all times during the study, except during oral temperature measurements or during a 15-minute break period in the middle of the study.

Population Size

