The number of samples required to understand the impact of environmental or physiological confounds on surface temperature is dependent on the variability in the core-to-surface temperature physiologic offset. The variability in core body temperature has been found to be close to 1F but note the research design proposed here is not dependent on normal person-to-person variability in core temperature because the temperatures obtained are all referenced to each individual's core temperature. To estimate the likely physiologic variability in the population, we can extrapolate based on surface temperature data taken by the primary thermographic system obtained over the past six months because this should be approximately the vector sum of variability in core temperature, measurement accuracy, and the physiologic variability. This data must be interpreted with caution, because these have been obtained with less control over environmental conditions and furthermore we do not know the core body temperature variability in the preliminary data population, but it can provide a reasonable error bound. This data shows a standard deviation of 1.11F (note, this value is obtained without *any* bias-to-normal algorithm, which appears to be a novel feature in this research), which would suggest the physiologic variability component is at most 0.48F, or half a degree. Therefore, in order to determine the sensitivity and specificity at detecting elevated temperatures of 1.8F (100.4F threshold) to within 20% (meaning, can we significantly distinguish 100.40 from 100.04F with the aforementioned standard deviation in a one-sided paired t-test), we require 28 participants. To account for possible data collection failures, we intend to recruit as many as 45 participants.

Data Collection

- Demographic and clinical data: minimal demographic and clinical data will be collected by interview with the participant at the time of the imaging studies including age, gender, any disease- or autonomic-modulating treatment, height, weight and any antipyretic medications in past 12 hours in order to allow adjustment for confounding factors. We do not intend to collect data on menstrual cycle due to the additional potential privacy concerns this will place on participants worried about this data which is significantly more sensitive than other data being collected.

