encompassing both areas. The desired target temperatures for the equilibration phase (Rooms D and E above) are 60F and 80F (or 10F lesser than and 10F greater than the building's setpoint), while the desired target temperatures for the blinded temperature phase (Rooms A, B and C) are 68, 75.6 and 83.2F, if the building's target temperature is 68F, otherwise these should be offset with the difference. To obtain these temperatures, three rooms require heating and one room requires cooling. Each of the heated rooms will have a 1500W space heater and the cooled room will have a flexible temporary doorway installed with ductwork to a portable air conditioning unit. A wall-powered thermostat directed to switch by a rectified PID controller is then used to regulate the on/off cycle of each system. The building's airflow via the ductwork into the room may be damped with assistance from building maintenance. An air temperature logging system is set up in each room and in a preliminary study, is used to obtain the time constant and thermal stability of the room with the associated heating and cooling equipment. The key requirement for a suitable room is that the thermal stability must remain within 1C (1.8F) of a single value near the desired setpoint temperature for 10 minutes. Note, during both phases, it is unlikely these exact setpoints will be achieved at all times due to repeated opening and closing of doors, but fortunately this is not essential because ultimately the analysis is dependent on induced surface temperatures and the resulting induced core temperatures will be calculated for each subject based on the actual blinded temperature and the temperature of the room the IR thermometry is done within.

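### The balanced oral-fever subset will often have too few fevers to test, and comparing its p-value with the whole set's can point the opposite way to the association

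*Combined protocol and SAP*

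**What the plan says.** D. Analyses first plans a significance test of the linear correlation between oral and imaging temperatures below threshold. It continues: "A subset of the data consisting of equal parts of over-threshold (fevers, by oral temperatures) and under-threshold participants will be tested for significance", with "this significance level compared with that of the whole set". The second sentence does not repeat the word correlation, but that is the natural reading. The fever threshold is 38C (100.4F). The section gives no minimum number of oral fevers, no fallback, and no rule for drawing the under-threshold half.

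Four other places bear on this:

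- A. Introduction: "A new method, used in this study, allows the objective manipulation of face temperatures". It also gives healthy-adult oral temperatures as having "a standard deviation of approximately 1F (0.6C) and averages ranging from 97.9F to 98.6F".
- Controlled Temperature Rooms: "ultimately the analysis is dependent on induced surface temperatures and the resulting induced core temperatures will be calculated for each subject". The induced core temperature is therefore a calculated quantity.
- Study Population: "Participants will be recruited from the population of summer students, faculty and staff at St Olaf college" and from an affiliated email list. Fever is neither sought nor an exclusion.
- Population Size: 28 participants are required, and "we intend to recruit as many as 45 participants".

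**The concern.** Half of the subset must be people whose oral temperature is over threshold. The experimental manipulation acts on the skin of the face, and nothing in the documents says that it is meant to raise oral temperature. The rule therefore depends on naturally occurring fevers in a small campus sample. The Introduction itself says that such fevers are hard to find even in emergency departments.

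Two things are at stake. The pre-specified test may not be computable. If it is, its p-value comes from a handful of people and is set beside one from the whole sample. A reader could take the larger p-value as a property of the device when it mainly reflects the number of people.

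**Working it through.** **Inputs.** Threshold 100.4F (D. Analyses). Oral mean 97.9–98.6F, SD 1F or 0.6C = 1.08F (Introduction). N = 28 or 45 (Population Size). Assumed: normal distribution, one oral value per participant, no effect of room air on it, two-sided 5% level.

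**The plan's own figures.** The plan states no expected number of oral fevers, so there is none to reproduce. Two related figures do reproduce:

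- Population Size says "which would suggest the physiologic variability component is at most 0.48F": √(1.11² − 1²) = √0.2321 = 0.48F.
- The room targets follow from 7.62F of air per 1.8F of simulated core: 68 + 7.62 = 75.6F and 68 + 15.24 = 83.2F. The designed shifts are thus 0, 1.8 and 3.6F.

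**Step 1: expected oral fevers.** p = 1 − Φ((100.4 − mean)/SD), and the count X is Binomial(N, p). The subset needs X ≥ 2. X = 0 leaves nobody, and X = 1 leaves two people and zero degrees of freedom. P(X ≤ 1) = (1 − p)^N + Np(1 − p)^(N−1).

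| Mean, SD (F) | p | Expected, N=28 | P(X≤1), N=28 | Expected, N=45 | P(X≤1), N=45 |
|---|---|---|---|---|---|
| 97.9, 1.00 | 0.0062 | 0.17 | 99% | 0.28 | 97% |
| 97.9, 1.08 | 0.0103 | 0.29 | 97% | 0.46 | 92% |
| 98.6, 1.00 | 0.0359 | 1.01 | 73% | 1.62 | 52% |
| 98.6, 1.08 | 0.0478 | 1.34 | 61% | 2.15 | 36% |

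As a check that does not use the normal tail, the emergency-department yield in the Introduction (under 100 of at least 2,000, so under 5%) gives under 28 × 0.05 = 1.4 and under 45 × 0.05 = 2.25. When X ≥ 2, between 90% and 100% of studies have 2–4 fevers, which means 4–8 people.

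**Step 2: the p-value comparison.** For a correlation, t = r√((n − 2)/(1 − r²)). Holding r at 0.90 gives p = 0.10 at n = 4, 0.015 at n = 6, 0.002 at n = 8 and below 0.0001 at n = 28.

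Holding r fixed leaves out the wider range that balancing creates. A simulation of 20,000 studies includes it (N = 45, mean 98.6F, SD 1.08F, no room effect). Medians by number of oral fevers:

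| Imaging noise | Fevers (subset n) | r, subset / whole | p, subset / whole |
|---|---|---|---|
| 0.48F | 2 (4) | 0.976 / 0.915 | 0.024 / 1e-18 |
| 0.48F | 4 (8) | 0.959 / 0.926 | 0.0002 / 8e-20 |
| 1.11F | 2 (4) | 0.883 / 0.699 | 0.12 / 1e-7 |
| 1.11F | 4 (8) | 0.828 / 0.727 | 0.011 / 2e-8 |

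The association is stronger in the subset while its p-value is weaker. Over participant-level r of 0.5–0.9, the subset p exceeded the whole-set p in 95–100% of computable cases.

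**Step 3: why r alone is not a sufficient replacement.** Pearson r is unchanged by linear compression. Simulated setting: 28 participants, shifts 0/1.8/3.6F, offset SD 0.48F, assumed visit noise 0.3F. Readings taken as they are and correlated with simulated core give r of about 0.95 and about 92% sensitivity at 100.4F. The same readings compressed to 20% around 98.6F give the identical r and 0% sensitivity. The slope separates them: about 1 against about 0.2.

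**The case against.** **Balancing has a purpose.** The Introduction warns that correlation misleads when a variable varies little, and says that an evaluation should reach real fevers if bias-to-normal is to be detected. Balancing does widen the range and does raise r. This stands: the aim is sound, and a claim that the subset carries no information would go too far. The fault lies in depending on oral fevers and in comparing p-values.

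**The counts rest on assumptions.** Each participant gives three oral readings in the blinded phase. Suppose anyone with one reading over threshold counts, and the three readings are treated as fully independent, which is generous. Then 0.5–3.8 of 28 and 0.8–6.2 of 45 are expected, with at most one in 9–91% and 1–80% of studies. The Introduction also says that oral thermometry can be sensitive to air temperature, without giving a size. If every participant's value rose by an assumed 0.5F, p would be 2.3–11.4%. That means 0.6–3.2 of 28 and 1.0–5.1 of 45, with at most one in 15–87% and 3–73%. In the favourable corner the test would usually be computable; in the unfavourable corner it would not. The comparison of p-values remains on the wrong scale in either case.

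**Power.** A reader might infer that the subset test nearly always fails when it is run. It does not: at r = 0.90 it is significant in 78–85% of computable cases.

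**Reach.** A reader might also infer that scarce oral fevers undermine the study's sensitivity and specificity. The documents do not support that. Those labels come from the room-to-scanner air temperature difference, and neither they nor the check for a 50% split around the threshold need an oral fever.

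**Conclusion.** The point holds and is minor. As written, the subset test has no testable subset in 61–99% of studies at N = 28 and 36–97% at N = 45. These figures assume normal oral temperatures with the protocol's mean and SD, one value per participant, and no room effect on oral readings; relaxing the last two widens the ranges downwards. When the test can be run, usually on 4–8 people, the p-value comparison almost always favours the whole set because of its size, even where the subset r is higher. That second conclusion does not depend on the exact fever count while the subset stays this small. The analysis is supplementary, and the room-label sensitivity and specificity analysis is unaffected.

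**What to change.** In D. Analyses:

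1. Remove the comparison of significance levels.
2. Report the below-threshold and whole-set oral–imaging relationship as slope and r, with 95% confidence intervals that allow for repeated visits by the same person. Mark any oral fevers on the scatter plot.
3. Do not run the oral-fever balanced subset as a significance test. If enough oral fevers occur, by a minimum count stated in advance, show it descriptively as slope and r with intervals. As a guide, at r = 0.90 the Fisher-z 95% interval is −0.45 to 1.00 at n = 4 and 0.53 to 0.98 at n = 8.
4. If a wider-range contrast is wanted, base it on each visit's simulated core temperature (own oral plus room-induced shift). Report the slope (1 means no compression) or agreement with a participant-level bootstrap interval, not r alone. Averaging over shifts of 0, 1.8 and 3.6F, about 37–50% of visits lie at or above 100.4F: 31–42 of 84 visits, or 50–68 of 135.

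Cost: a few sentences, no new data, and modest code for item 4. The downside of item 4 is that its result is conditional on the pilot coefficient, which the plan says may be refined, and on the delay between leaving the room and the scan. Both should be stated with the result.
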